## **8.4 PHARMACODYNAMICS AND CORRELATIVE BIOMARKERS**

Whole blood will be collected during study as specified in the SoA and the study-specific Laboratory Manual. The main objective is to characterize the immune phenotype and function of the subject PBMC before each SUPLEXA administration by PBMC composition and cytokine levels in peripheral blood samples, as well as immunophenotyping (e.g., PBMC profiling, cytokine, and tumour pharmacodynamics marker assessment). Additional, chronological blood samples will also be evaluated as above.

Samples may be stored at a facility selected by the Sponsor, to enable downstream batch analysis, to the maximum limit permitted according to local regulations following subject's last visit for the study.

Residual blood samples may be stored for identification of factors or profiles that correlate with measures of response to study intervention.

For more details on the procedures, please refer to the study-specific Laboratory Manual.

## 9 STATISTICAL CONSIDERATION

### 9.1 SAMPLE SIZE DETERMINATION

Approximately 60 subjects will be enroled with a cap of about 8 subjects per individual tumour type (e.g., melanoma, breast, prostate, lung, haematological malignancies, etc.). If promising anti-tumour activity coupled with acceptable safety is observed, overall sample size and/or cap per tumour type may be expanded.

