### **Number of Subjects**

Up to 60 subjects may be enroled with a cap of about 8 subjects per individual tumour type with a prioritization and focus on melanoma, breast, prostate, lung, and haematological malignancies. If promising anti-tumour activity coupled with acceptable safety is observed, overall sample size and/or cap per tumour type may be expanded.

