#### 9.3.1 General

Statistical analyses will be performed using SAS® v9.4 or higher (SAS Institute, Cary NC, USA) and all analysis will be described in the SAP finalized before database lock.

The standard summary statistics for continuous variables are sample size (n), mean, standard deviation (SD), median, minimum, and maximum. The standard summary statistics for categorical variables are frequencies and percentages. Time to event variables will be summarized using the Kaplan-Meier method. Where confidence limits are appropriate, the confidence level will be 95% (two-sided), unless otherwise stated.

Individual data (including relevant derived variables) will be presented by parameter in listings. Results of statistical analyses, descriptive summary statistics and supportive listings will also be presented.

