### 9.3.2 Efficacy Analysis

#### Solid Tumour Cohort

The secondary endpoint of ORR will be defined as the proportion of subjects with BOCR of either a CR or PR as assessed by the Investigator using RECIST v1.1 in the Response Evaluable Population as both unconfirmed or confirmed status. ORR will be reported as a proportion along with the corresponding 2-sided 95% Clopper-Pearson exact CI.

A sensitivity analysis of the primary endpoint will be performed in the Response Evaluable Population.

Other secondary and exploratory endpoints are defined as follows for the whole cohort or analysed by tumour type:

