#### **9.3.5 Interim Analysis**

Open label study and no interim analysis is planned.

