#### **9.3.6 Data Safety Monitoring Board (DSMB)**

The DSMB, a specific independent committee for the study with external representation composed of at least 3 members and include experts in the field of oncology and clinical studies, or biostatistics. Other members may be invited as needed. The DSMB will regularly monitor overall safety on an unblinded basis, as well as general aspects of study conduct, to ensure that the benefits and risks of study participation remain acceptable.

The DSMB will evaluate all relevant toxicity data and confirm that the principal investigator is reporting all serious, unexpected, or other related toxicities to the regulatory authorities.

During the conduct of the study, the DSMB will periodically be asked to advise the Sponsor regarding modification, continuation, or discontinuation of the study based on the review of the study safety data. Efficacy data will not be provided to the DSMB.

Details on the composition of the DSMB, meeting structure, schedule, and procedures, the content and format of DSMB reports, and other relevant details will be determined in consultation with DSMB members and detailed in a separate DSMB charter.

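### If a tumour type is expanded because of its responses and the triggering subjects stay in its ORR, that ORR is biased upward, and the plan does not provide for this

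*Combined protocol and SAP*

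**What the plan says.** Section 9.1 sets the size: "Approximately 60 subjects will be enroled with a cap of about 8 subjects per individual tumour type". The synopsis says the same with a slightly different opening: "Up to 60 subjects may be enroled with a cap of about 8 subjects per individual tumour type". Both then allow growth, in Section 9.1's words: "If promising anti-tumour activity coupled with acceptable safety is observed, overall sample size and/or cap per tumour type may be expanded". Neither place gives a number of responders, the number of subjects at the look, the timing, the decision-maker or a maximum expanded size.

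Section 9.3.5 reads: "Open label study and no interim analysis is planned". Section 9.3.6 adds: "Efficacy data will not be provided to the DSMB". No independent body is therefore assigned the activity review on which an expansion would rest.

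For the solid tumour cohort, Section 9.3.2 states: "ORR will be reported as a proportion along with the corresponding 2-sided 95% Clopper-Pearson exact CI". Section 9.3.1 sets the default: "the confidence level will be 95% (two-sided), unless otherwise stated". Nothing in Section 9 separates subjects enrolled before an expansion from those enrolled after it, adjusts the estimate or the interval, or adds a caveat about selection.

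**The concern.** Enlarging a tumour type because its first subjects responded is a sample-size decision that depends on efficacy, and it can be taken separately in each type. It is an interim look in substance, although Section 9.3.5 says none is planned. Types with a lucky start are the ones that grow. If their early responders are then counted in the final proportion, the estimate carries that luck with it.

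At stake is how activity is read in the types that look most interesting. Section 4.2 says the study's assessments, disease response among them, serve to determine the recommended Phase 2 dose for further studies. The relative inflation is largest where the true ORR is low, which is where a false signal would mislead most.

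**Working it through.** **The plan's own figures.** The total of about 60 cannot be reproduced. Section 9.1 gives no null or target rate, precision goal, alpha or power. The only arithmetic available is 60/8 = 7.5 full tumour types.

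**Inputs.**
- From the plan: about 8 subjects per type before expansion; two-sided 95% Clopper-Pearson interval.
- Assumed, because the documents are silent: true ORR p; expansion if at least r of the first 8 respond; n2 subjects added; seven types.
- Range examined: p = 5%, 10%, 20%, 30%; r = 1, 2, 3; n2 = 8, 12, 22, giving 36 combinations. The central case is r = 2, n2 = 12 (final n = 20).

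**Step 1: bias given expansion.** Let X1 ~ Bin(8, p) and X2 ~ Bin(n2, p). The reported ORR is (X1 + X2)/(8 + n2), and

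bias given expansion = [8/(8 + n2)] × (E[X1/8 | X1 ≥ r] − p).

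This is above zero for every r ≥ 1 and 0 < p < 1. For r = 2, E[X1 | X1 ≥ 2] = (8p − P(X1 = 1))/P(X1 ≥ 2). With n2 = 12:

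| True ORR | P(X1 = 1) | P(expand) | E[X1 given expansion] | Reported ORR, on average |
|---|---|---|---|---|
| 5% | 0.2793 | 0.0572 | 2.108 | (2.108 + 0.6)/20 = 13.5% |
| 10% | 0.3826 | 0.1869 | 2.233 | (2.233 + 1.2)/20 = 17.2% |
| 20% | 0.3355 | 0.4967 | 2.546 | (2.546 + 2.4)/20 = 24.7% |

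Over all 36 combinations the bias is upward, from +0.5 points (p = 30%, r = 1, n2 = 22) to +16.7 points (p = 5%, r = 3, n2 = 8).

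**Step 2: how often it would arise.** P(at least one of seven types expands) = 1 − (1 − P(expand))^7. For r = 2 this is 1 − (1 − 0.0572)^7 = 33.8% at a true 5%, and 1 − (1 − 0.1869)^7 = 76.5% at a true 10%, with the same true rate in every type.

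**Step 3: interval coverage given expansion.** At p = 5% and n = 20, the exact lower limit is 3.2% for 3 responders and 5.7% for 4, so the interval misses the truth once there are 4 or more. Given expansion at r = 2, that has probability 15.6%, so coverage is 84.4%. The same calculation gives 95.0% at p = 10% and 98.0% at p = 20%. Over the 36 combinations, 26 reach 95% (to three decimals). The ten that do not all have a true ORR of 5% or 10% and r = 2 or 3; the lowest is 51% (p = 5%, r = 3, n2 = 12).

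**Step 4: averaging over expanded and unexpanded types.** For p = 10%, r = 2, n2 = 12: 0.1869 × 0.1717 + 0.3826 × (1/8) = 0.0321 + 0.0478 = 8.0%. The average over all types is therefore below the truth.

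**Step 5: whole-cohort ORR** (simulation, seven types, r = 2, n2 = 12). If every type has the same true rate, the mean pooled ORR is 4.8%, 9.6% or 19.5% for a true 5%, 10% or 20%, a slight fall. With five types at 5% and two at 30%, equal weighting gives (5 × 5 + 2 × 30)/7 = 12.1%, while the pooled ORR averages 15.6%. The cause is the mix: expected sizes are 8 + 12 × 0.057 = 8.7 subjects in a low-rate type and 8 + 12 × 0.745 = 16.9 in a high-rate type.

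**The case against.** The strongest reply is that this is a small, open-label, non-comparative Phase 1 study. DLTs and adverse events are primary, ORR is secondary, and there is no null rate or test to protect. Expansion is optional and also requires acceptable safety. All of that stands, and it limits the severity.

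A second reply is that ORR by tumour type is not expressly planned. The by-type wording, "Other secondary and exploratory endpoints are defined as follows for the whole cohort or analysed by tumour type", introduces the other endpoints, the exact interval is specified only for the solid tumour cohort, and Section 9.3.2 does not say how expansion subjects are handled. This also stands: a pooled ORR per type is an inference. It is a natural one, because enlarging a single type has little purpose unless its result is read by type.

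A third reply is that a separate SAP may settle the matter. Section 9.3 requires that SAP only before database lock, by which time open-label responses could already have driven expansions. A rule written then would not be prespecified.

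A reader might also infer three stronger conclusions that the documents do not support:
- **The exact interval fails in general.** It does not. Clopper-Pearson is conservative, and coverage given expansion stays at about 95% or above in most of the assumed cases.
- **Whole-cohort ORR is inflated.** It is only if true rates differ between types; with equal rates it falls slightly.
- **ORR is biased upward overall.** The upward bias is conditional on expansion; averaged over all types it is downward.

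**Conclusion.** The point holds in a conditional form. If a type is expanded on its responses and the triggering subjects stay in its ORR, that ORR overstates the true rate. The direction needs no assumption beyond a response-based trigger. The size rests on an assumed trigger of 2 in 8 and expansion to 20: bias of +8.5, +7.2 and +4.7 points at a true 5%, 10% and 20%. Other triggers and sizes within the assumed range give +0.5 to +16.7 points. Loss of interval coverage and a shift in whole-cohort ORR are possible consequences, not certain ones. The rating is should-fix: the bias affects how activity is interpreted, not a primary endpoint or an error rate.

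**What to change.** **Section 9.3.2.** For any tumour type expanded on observed activity:
- Report ORR with its exact interval separately for subjects enrolled before and after the expansion decision.
- Treat the post-expansion ORR as the estimate free of selection by the trigger, provided the expansion size is not changed again on later responses.
- Label any pooled ORR for that type as subject to selection.
- Show whole-cohort ORR alongside results by tumour type, so that a change in mix is visible.

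**Section 9.3.5.** State that expansion under Section 9.1 is a look based on efficacy, and record the date of each expansion decision and the data on which it rested.

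Fixing a numeric trigger and a maximum size in advance would let the selection be quantified. That is a further design choice, and this point does not depend on it.

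**Cost.** Some wording, a decision record and a few table rows; no extra subjects or procedures. The ORR highlighted for an expanded type will tend to be less favourable and its interval wider. For example, an observed 25% has an exact 95% interval of 5.5% to 57.2% with 3 of 12, against 8.7% to 49.1% with 5 of 20.

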### 9.2 POPULATION FOR ANALYSES

For purposes of analysis, the following populations are defined:

Population	Description
DLT evaluable Population	All subjects who receive at least 1 dose of study intervention and experience a DLT.
Safety Analysis Set	All subjects who receive at least 1 dose of study intervention.
Response Evaluable Population	All subjects who receive at least 1 dose of study intervention and have measurable disease at baseline and at least one post-baseline tumour assessment per RECIST v1.1.

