### 3 OBJECTIVES AND ENDPOINTS

Objectives	Endpoints
Primary	

 
To assess safety and tolerability of SUPLEXA in subjects with malignant solid tumour and haematologic malignancies.
 
	
 
Incidence of dose limiting toxicities (DLTs) (as described in Section 6.5.1).
 
Incidence of adverse events (AEs), and serious adverse events (SAEs) overall, by severity, by relationship to each study intervention, and those that led to discontinuation of study intervention.
 

Secondary 
 
Solid tumours cohort: To assess the efficacy of SUPLEXA in subjects with malignant solid tumour as assessed by the Investigator based on response evaluation criteria in solid tumours (RECIST) v1.1 or by changes in tumour-derived blood biomarkers.
 
Haematologic malignancies cohort: To assess the efficacy of SUPLEXA in subjects with haematologic malignancies (multiple myeloma, lymphoma, and chronic lymphocytic leukemia).
 
	
 
Objective response rate (ORR) defined as the proportion of subjects with best overall response (BOCR) of either a complete response (CR) or partial response (PR).
 
Time to Progression (TTP).
 
Objective response rate as defined by standard of care.
 

Exploratory 
 
Exploratory efficacy outcomes
 
	
 
Duration of Response (DOR)
 
Time to Response (TTR)
 
Clinical Benefit Rate (CBR) defined as CR + PR + stable disease (SD).
 
Progression-free Survival (PFS).
 
Overall Survival (OS).
 
Solid tumours cohort: Change in plasma biomarkers.
 
Haematologic malignancies cohort: Response-relationship with correlative biomarkers in blood and bone marrow including immunophenotyping of circulating PBMC and/or bone marrow, gene expression, mutational analysis.
 

Objectives	Endpoints

 
• To evaluate anti-tumor activity of SUPLEXA by based on modified RECIST v1.1 for immune based therapeutics (iRECIST)
 
	
 
• iORR
 
• iPFS
 
• iDOR
 
• iDCR
 

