##### **4.1.2.1 First 3 SUPLEXA infusions (from batch 1)**

Initially, SUPLEXA will be administered at Day 1 (baseline), Week 1 and Week 2 (Section [1.2](#), [Figure 2](#)). The first 3 subjects in each cohort will be monitored closely at the clinic after each of these 3 weekly infusions with follow-up phone calls as described below.

The first 3 subjects in each cohort will be enroled and subsequently dosed in a staggered manner, at least 1 week apart to allow for evaluation of safety. These subjects will be monitored for safety in the clinic for 6 hours after each of the 3 weekly infusions and be contacted by phone on a daily basis (weekdays) between these weekly infusions and for up to 5 days post final treatment. While the Investigator will review safety data on a continual basis, the DSMB will have an opportunity to review the first 3 patients in each cohort who receive at least 3 doses of SUPLEXA to further evaluate safety and make a recommendation to the Sponsor concerning continuation or enrolment, pause in enrolment or study termination. While the DSMB reviews the data from the first 3 subjects in each cohort, additional subjects will be screened and enroled into each cohort. These additional subjects will not be dosed until the first 3 subjects in their cohort are cleared by the DSMB. These subjects will be monitored closely at the clinic for at least 3 hours after each of these 3 weekly infusions with follow-up phone calls every 2 business days between treatments and for up to 5 days post the 3rd infusion. If any of these subjects experience an adverse event of Grade 3 or greater, the longer in-clinic monitoring window of 6 hours post each of the first 3 weekly infusions and daily calls will be reimplemented as done for the first 3 subjects. During the observation period post SUPLEXA administration, subjects will be monitored for any AEs and immediate post infusion reaction(s) every 90 minutes.

The first 15 subjects in the trial will be evaluated for DLTs twice, 1 week after the 1st and 2nd dose (prior to administration of 2nd and 3rd dose, respectively). The DLT criteria and DLT assessment period(s) are defined in Section [6.5](#).

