#### 4.2 SCIENTIFIC RATIONALE FOR STUDY DESIGN

This FIH study will assess the safety and preliminary efficacy of repeated IV doses of SUPLEXA in the intended study population (subject with measurable solid tumours and

haematologic malignancies) in a single-arm, open-label, monotherapy study design. The study includes assessments of safety and tolerability, disease evaluation by RECIST v1.1 (solid tumours) and disease response (haematologic malignancies) as well as pharmacodynamics / biomarker assessment, and immunogenicity characterizations, to determine the recommended Phase 2 dose (RP2D) of SUPLEXA for further clinical studies.

As this is FIH study, to avoid exposing subjects to any unexpected toxicity, the study will include a staggered enrolment design whereby 3 subjects will be enroled, SUPLEXA manufactured and stored, then doses will be given in a staggered manner, at least one week apart to allow evaluation for safety before lining the remaining of the subjects. The first 15 subjects led and treated will be evaluated for DLTs after the first and second infusion.

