## 6.5 DOSE LIMITING TOXICITY CRITERIA

A DLT is defined as the occurrence or start of any of the events listed below during the treatment of the first 3 subjects in each cohort that are assessed as related to study intervention (SUPLEXA) by the Investigator or the Sponsor. An AE should not be considered as a DLT if it can reasonably be attributed to underlying disease, disease progression, concomitant medications, or other extraneous causes. Worsening of pre-existing medical illness could be due to study intervention and should not be excluded from consideration as a DLT.

The first 15 subjects will be assessed for DLT. For each subject, the DLT assessment period will comprise of 2 parts as follows (Refer to [Figure 5](#)):

- The first DLT assessment period – 1 week after the first dose (prior to administration of the second dose).
- The second DLT assessment period - 1 week after the second dose (prior to the administration of the 3rd dose)

Subjects who withdraw before the end of the DLT assessment period for reasons other than DLTs will be replaced.

All toxicities will be graded by the local site Investigator using National Cancer Institute (NCI) common terminology criteria for adverse events (CTCAE) v5.0.

The following will be considered DLTs:

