#### **6.5.1 Dose Modifications and Individual Stopping Rules due to DLT**

All eligible subjects are planned to receive a minimal cumulative dose of approximately 7.5 billion cells of SUPLEXA administered as target of 2.5 billion cells per individual SUPLEXA doses. The first 3 doses will be administered at least 1 week apart (unless delayed due to DLTs as described below) at Day 1 (baseline), Week 1 and Week 2.

During the study, the cumulative dose of study intervention will not be modified unless triggered by rules governing DLT (as described below); that is, subjects experiencing a DLT which does not resolve within 3 weeks or 2 DLTs may only receive 1 or 2 infusions, each 2.5 billion cells (for these subjects, cumulative dose may range between 2.5 billion cells to 5.0 billion cells).

[figure not shown]
The DSMB will convene to review all available data collected during the DLT assessment period(s) including Investigator's impressions and provide an additional layer of oversight. The DSMB will make recommendations to the Sponsor on enrolment modifications.

The rules below will apply independently to the solid tumours and haematologic malignancies in parallel and for each subject in the study.

1. Enrol a subject and administer 1st dose on Day 1. Assess for DLTs during the first DLT assessment period (1 week post 1st infusion).
  - a) No DLT, continue to 2nd dose at Week 1 (Day 8) – refer to item 2 below,
  - b) Subject experienced a DLT (per DLT criteria in Section 6.5) and the event resolved within 3 weeks to baseline levels (Grade 1 or lower)?
    - i) Yes, continue to 2nd dose – refer to item 2 below
    - ii) No, permanently discontinue study intervention and subject will continue to be followed-up as part of the study (unless withdraw consent and start other anti-cancer therapies) as described in Section 7.2.
2. Administer 2nd dose. Assess for DLTs during the 2nd DLT assessment period (1 week post 2nd infusion)
  - a) No DLT, continue to 3rd dose – refer to item 3 below

- b) Subject experienced a DLT (per DLT criteria in Section 6.5)
  - i) If first occurrence of DLT and the event resolved within 3 weeks to baseline levels (Grade 1 or lower)?
    - Yes, continue to 3rd dose – refer to item 3 below

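### Section 9.2 limits the DLT evaluable population to subjects who had a DLT, so DLT incidence has no usable denominator, and the sections disagree on who is assessed

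*Combined protocol and SAP*

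**What the plan says.** The first-listed primary endpoint in Sections 1.1 and 3 is "Incidence of dose limiting toxicities (DLTs) (as described in Section 6.5.1"). Section 9.2 names one population for DLTs: "All subjects who receive at least 1 dose of study intervention and experience a DLT". The Safety Analysis Set, defined in the same table, is everyone dosed at least once. Section 9.3.3 bases adverse events, laboratory values and other safety data on the Safety Analysis Set and does not mention DLTs.

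On who is assessed, the current text gives several answers:

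- Section 6.5, in defining a DLT, refers to "events listed below during the treatment of the first 3 subjects in each cohort". With two cohorts that is 6 subjects.
- The next paragraph of Section 6.5 says "The first 15 subjects will be assessed for DLT".
- Section 4.1.2.1 agrees with 15: "The first 15 subjects in the trial will be evaluated for DLTs twice". So does Section 4.2: "The first 15 subjects led and treated will be evaluated for DLTs after the first and second infusion".
- Section 6.5.1, which the endpoint cites, introduces the DLT rules with "The rules below will apply independently to the solid tumours and haematologic malignancies in parallel and for each subject in the study".
- Section 1.1 (Treatment Period) refers to the first subjects under Amendments 2 and 3 and gives no number.

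Section 6.5 also has a replacement rule: "Subjects who withdraw before the end of the DLT assessment period for reasons other than DLTs will be replaced".

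**The concern.** An evaluable population for an incidence has to contain subjects who could have had the event and did not. The Section 9.2 definition makes membership depend on the outcome, so every subject who passes both DLT periods cleanly is left out. The set's name, and the absence of any other assignment, invite a programmer to use it as the denominator for a primary safety endpoint.

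Correcting that sentence alone would not settle the rate, because the number of assessed subjects is 6, 15 or about 60 depending on the section read. In an open-label study, a denominator chosen after the data are known is open to challenge. If few or no DLTs occur, the choice of denominator largely determines what the trial can claim about tolerability.

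**Working it through.** The plan states no DLT rate, target rate or DLT-based sample size, so there is no figure of its own to reproduce. The check applies the definitions directly.

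**Inputs**

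- Definition of the DLT evaluable population: Section 9.2.
- Assessed subjects: 3 × 2 = 6 (Section 6.5, definition); 15 (Sections 4.1.2.1, 4.2 and 6.5); about 60 (Section 6.5.1, every subject, with planned enrolment from Section 9.1). The last assumes that all 60 are dosed and assessed.
- Confidence level: 95% two-sided (Section 9.3.1). Exact Clopper-Pearson limits are the reviewer's choice here; the plan specifies them for ORR and sets no interval for DLT incidence.
- Data so far: more than 15 subjects enrolled, each given 3 to 6 doses, with no treatment-related adverse event (Section 2.3.1; Section 4.3 says the same of the ongoing study). A DLT must be assessed as related (Section 6.5), so the implied count at that date is zero.

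**Step 1: the definition as written.** If d subjects have a DLT, the population has size d and the incidence is d/d.

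- d = 0: 0/0, undefined.
- d = 1: 1/1 = 100% (95% CI 2.5% to 100%).
- d = 2: 2/2 = 100% (15.8% to 100%).
- d = 3: 3/3 = 100% (29.2% to 100%).

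On the data reported in Section 2.3.1 the set is empty.

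**Step 2: a set that includes subjects without a DLT.** For zero events in n subjects the exact upper limit is 1 − 0.025^(1/n):

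- n = 6: 1 − 0.025^(1/6) = 45.9%
- n = 15: 1 − 0.025^(1/15) = 21.8%
- n = 60: 1 − 0.025^(1/60) = 6.0%

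For one or two events:

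| DLTs | n = 6 | n = 15 | n = 60 |
|---|---|---|---|
| 1 | 16.7% (0.4 to 64.1) | 6.7% (0.17 to 31.95) | 1.7% (0.04 to 8.9) |
| 2 | 33.3% (4.3 to 77.7) | 13.3% (1.7 to 40.5) | 3.3% (0.4 to 11.5) |

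**Step 3: how often the set would be empty.** The chance of no DLT is (1 − p)^n. At assumed true rates of 5%, 10% and 20% it is 73.5%, 53.1% and 26.2% with 6 assessed, and 46.3%, 20.6% and 3.5% with 15 assessed.

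**Step 4: what was probably meant.** The replacement rule in Section 6.5 replaces subjects who leave the window early for reasons other than a DLT. That makes sense only if subjects who finish the window without a DLT count. The rule therefore points to a set made up of those who had a DLT plus those who completed assessment.

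**The case against.** Several objections carry weight.

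- **The denominator is never stated.** No sentence says DLT incidence is computed on this set. DLTs are adverse events, and Section 9.3.3 puts adverse event frequency on the Safety Analysis Set. It is therefore correct that the 100% or 0/0 result is conditional. But Section 9.3.3 is silent on DLTs, and using all dosed subjects would add people whom Sections 4.1.2.1, 4.2 and 6.5 place outside the assessed group. On this reading a primary endpoint has no stated denominator, which also needs correcting.
- **The SAP may put it right.** Section 9.3 says the SAP will describe the populations and will prevail over that section. No SAP text in the document supplied makes the correction, and Section 9.3 also requires major modifications to be reflected in a protocol amendment. A corrected population in the SAP would still leave Sections 4 and 6 in conflict.
- **No trial decision uses a DLT proportion.** This is true. Section 6.5.1 works subject by subject, and the Section 7.1 hold is a count. The damage is to the reporting of one primary endpoint.
- **The all-subjects reading is the weakest.** Section 6.5.1 governs individual dosing and does not say who enters the incidence analysis. That is fair, but it is the section the endpoint cites, so a reader can reasonably arrive there. Section 1.1 is silent on the number and does not contradict the others.
- **Zero DLTs is not assured if all 60 count.** This stands. If 45 subjects remain (60 − 15), the chance of no further DLT is 0.99^45 = 64%, 0.98^45 = 40% or 0.95^45 = 10% at assumed rates of 1%, 2% or 5%. The case for calling zero likely is strongest for the 6- and 15-subject readings, whose windows appear to have closed.

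**Conclusion.** The concern holds. The Section 9.2 set is the numerator of DLT incidence. As a denominator it yields 100% or 0/0 and nothing else, and no other denominator is named for this primary endpoint. The conflict over who is assessed is in current text, with Section 6.5 contradicting itself in consecutive paragraphs.

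With zero DLTs, the upper 95% limit ranges from 6.0% to 45.9% across the three readings. The range rests on exact binomial limits and, for its lower end, on all of about 60 subjects being dosed and assessed. The 100% or 0/0 result rests on using the Section 9.2 set as the denominator. This must be fixed before analysis.

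**What to change.** 1. In Section 9.2, redefine the DLT evaluable population as subjects designated for DLT assessment who are dosed at least once and either experience a DLT or complete both DLT assessment periods.
2. In Section 9.3.3, add a sentence naming this set as the denominator for DLT incidence, preferably with an exact 95% confidence interval. Carry both changes into the SAP.
3. Reconcile Sections 1.1 (Treatment Period), 4.1.2.1, 4.2, 6.5 and 6.5.1 so that they identify the same DLT-assessed subjects. Then check that the DLT-based hold in Section 7.1, which is worded in terms of study subjects, is consistent with the result. Which subjects are assessed is for the sponsor to settle; no count or stopping rule is proposed here.

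The cost is a corrected definition, one added sentence and reconciliation of five places. No extra patients are needed. If the reconciled text covers 6 or 15 subjects, no new data are needed. If it covers every subject, the sponsor should confirm that DLT status is recorded for those after the first 15, or can be derived from their graded and causality-assessed adverse events.
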